4.2 Exclusion Criteria

A subject must meet none of the following exclusion criteria to be eligible for the study:

Medical Conditions

1. Pain anywhere else in the body which is greater than or equal to OA pain in the index knee, or likely to interfere with subject's assessment of pain throughout the study, as judged by the Investigator
2. History or presence on imaging of knee arthropathy (osteonecrosis, subchondral insufficiency fracture, rapidly progressive OA type 1 or type 2), recent fall, injury, or trauma affecting the index knee, ligament tear, neuropathic joint arthropathy, knee dislocation (patella dislocation is eligible), extensive subchondral cysts, Baker's cyst, evidence of bone fragmentation or collapse, or primary metastatic tumor with the exception of chondromas, or pathological fractures during the Screening Period
3. History or presence at Screening of non-OA inflammatory joint disease (e.g., rheumatoid arthritis, lupus erythematosus, psoriatic arthritis, pseudo-gout, gout, spondyloarthropathy, joint infections within the past 5 years, Paget's disease of the spine, pelvis, or femur, neuropathic disorders, multiple sclerosis, fibromyalgia, tumors or infections of the spinal cord, or renal osteodystrophy) or any condition that would interfere with the rating of OA pain
4. Recent arthroscopic surgery within 1 month of Screening; or has any planned surgery or procedure during the study

Concomitant Treatments

5. Use of monoamine reuptake inhibitors, tricyclic antidepressants, anticonvulsants, and/or serotonin norepinephrine reuptake inhibitors within 4 weeks prior to Screening.
6. Unwilling to discontinue current use of analgesic medication following Screening and to adhere to study requirements for rescue treatments (acetaminophen to be taken as needed with a maximum daily dose of 2500 mg), including, but not limited to, non-steroidal anti-inflammatory drugs (NSAIDs), opioids, selective cyclooxygenase 2 inhibitors, or combinations thereof, within 7 days or five half-lives of the drug prior to the Baseline Pain Assessment Period, whichever is longer

Note: only the rescue medication, i.e., acetaminophen, is allowed for OA pain in the knee; aspirin, at a dose of up to 81 mg per day, is allowed for prophylaxis of coronary and cerebrovascular events if stable for 30 days prior to Screening and the dose is expected to remain the same throughout the duration of the study

7. Use of immediate- or extended-release or controlled-release opioids (e.g., oxycontin), transdermal fentanyl, or methadone within 3 months prior to Screening

8. Use of opioids, for the treatment of pain other than OA of the knee, with a morphine equivalent dose of ≥ 30 mg per day for more than 2 days per week within 1 month prior to Screening
9. Use of systemic (i.e., oral) corticosteroids or intra-articular corticosteroids in any joint within 30 days prior to the screening visit (topical, intranasal, and inhaled corticosteroids are permitted)
10. Intra-articular injection of any approved (i.e., hyaluronic acid and corticosteroids) or unapproved treatments (e.g., platelet-rich plasma, capsaicin) into the index knee within 3 months of Screening
11. Physical/occupational/chiropractic therapy for the lower extremities or acupuncture for the lower extremities within 30 days of Screening, or the need for such therapy during the study

Medical History, Laboratory Studies, Vital Signs, and Electrocardiograms

12. Has current evidence, or history within the previous 12 weeks prior to Screening, of a serious and/or unstable psychiatric, neurologic, cardiovascular, respiratory, gastrointestinal, renal, hepatic, hematologic, endocrinologic, or other medical disorder, that in the judgment of the Investigator and/or Medical Monitor would jeopardize the safe participation of the subject in the study
13. Had a malignancy in the last year, with the exception of nonmetastatic basal cell of the skin or localized carcinoma in situ of the cervix
14. Has any clinically significant laboratory abnormalities at Screening that in the judgment of the Investigator or Medical Monitor would jeopardize the safe participation of the subject in the study. Has one or more clinical laboratory test values outside the range specified below at Screening or Baseline:
 - a. aspartate aminotransferase (AST) $\geq 1.5 \times$ the upper limit of normal range (ULN)
 - b. alanine aminotransferase (ALT) $\geq 1.5 \times$ ULN
 - c. total bilirubin (TBL) $>$ ULN range or has a known condition that is associated with hyperbilirubinemia (e.g., Gilbert's syndrome)
15. Has moderate or severe renal impairment (estimated glomerular filtration rate [eGFR] <60 mL/min/1.73 m² from screening clinical laboratory tests)
16. Has an ECG QTcF result >480 ms at Screening or Baseline
17. Has a history of uncontrolled hypertension, as defined by:
 - a. Systolic blood pressure ≥ 180 mmHg or diastolic blood pressure ≥ 100 mmHg at Screening or Baseline

- b. Systolic blood pressure of 160-179 mmHg or diastolic blood pressure of 100-109 mmHg at Screening or Baseline, AND a history of end-organ damage (including history of left ventricular hypertrophy, heart failure, angina, myocardial infarction, stroke, transient ischemic attack, renal failure, peripheral arterial disease and moderate to advanced retinopathy [hemorrhages or exudates, papilledema])
- c. Known clinical diagnosis of orthostatic hypotension
- d. Evidence of orthostatic hypotension at Baseline, defined as a decrease in systolic blood pressure ≥ 20 mmHg or diastolic blood pressure ≥ 10 mmHg after transitioning from the supine position (after resting for 5 minutes) to standing at 1 or 3 minutes. Subjects unable to stand may be assessed while sitting upright.

18. Congestive heart failure with New York Heart Classification of stage III or IV
([Appendix A](#))

19. Transient ischemic attack or cerebrovascular accident within the past 12 months prior to Screening, or myocardial infarction, or acute coronary syndromes within the past 6 months prior to Screening

20. Is suicidal at Screening or Day -1 as defined below:

- a. An answer of “yes” to C-SSRS questions 4 or 5 (current or over the last 6 months); OR
- b. Has attempted suicide within 1 year prior to Screening; OR
- c. Is actively suicidal in the Investigator’s judgment

21. Beck Depression Inventory-II (BDI-II) score ≥ 29 at Screening

22. Has a history of uncontrolled diabetes mellitus (DM), Type 1 or Type 2 DM, or glycosylated hemoglobin (HbA_{1c}) $> 8.0\%$ at Screening

23. Known history of human immunodeficiency virus (HIV) infection

24. Known history of infection with hepatitis B virus. Subjects with a history of hepatitis B are eligible if there is documentation of a negative test for hepatitis B surface antigen and a positive test for antibodies to the hepatitis B virus surface antigen

25. Known history of infection with the hepatitis C virus. Subjects with a history of hepatitis C are eligible if there is documentation of a negative hepatitis C virus RNA test

26. Has a known or suspected history of drug abuse or a recent (within the last 5 years) history of alcohol abuse

27. Use of medicinal or recreational marijuana or cannabidiol (CBD) within 1 month prior to Screening. The use of these substances are not allowed throughout the study

Other Criteria

28. Subject is unlikely to be able to swallow double-blind study drug (i.e., swallowing tablets 4 times per day, including two tablets at the first and third dosing)
29. Subject is unwilling or unable to comply with the use of the handheld devices
30. Has a significant sensitivity or allergic reaction to ACP-044 or its excipients, or rescue medication
31. Has participated in or is participating in a clinical research study evaluating ACP-044 or has received another investigational product within 30 days or 5 half-lives, whichever is longer, prior to Screening
32. Is an employee or is a family member of an employee of Acadia Pharmaceuticals Inc. or the clinical research site or the CRO administering this study

4.3 Screen Failures

Rescreening of a subject will be allowed, with the approval of the Medical Monitor.

Subjects may be rescreened following a COVID-19 infection as long as they have no sequelae from COVID-19 infection, per [Exclusion Criterion 12](#).

Subjects who enter the Baseline Pain Assessment Period will not be allowed to rescreen. Subjects who experience technical issues with the device and their pain scores were not assessed, may be rescreened and the Baseline Pain Assessment Period may be extended, if needed and with permission of the Sponsor.

The minimum information that will be captured for screen failures includes date informed consent is signed, demography, screen failure details, and any adverse event (AE)/serious adverse event (SAE).

4.4 Subject Withdrawal of Consent

In accordance with the Declaration of Helsinki and other applicable regulations, a subject has the right to withdraw from the study at any time, and for any reason, without prejudice to his or her future medical care.

If the subject decides to withdraw consent from all components in the study, this must be documented and no additional assessments will be performed. If the subject wants to discontinue treatment and agrees to the evaluations specified at the EOT/ET visit and/or at safety follow-up (whichever is applicable), as outlined in [Table S-1](#), the agreed assessments should be conducted. The subject's reason for wanting to discontinue treatment and the

agreement to continue with the applicable assessments for study termination must be documented.

4.5 Subject or Study Discontinuation

Subjects may be discontinued from the study for a number of reasons, including, but not limited to, those listed below:

- AE
- Death
- Lack of efficacy
- Lost to follow-up ([Section 4.6](#))
- Non-compliance with study drug
- Investigator decision
- Pregnancy
- Protocol deviation
- Study terminated by sponsor
- Use of prohibited medication
- Withdrawal of consent by subject
- Other

If at any time the C-SSRS results for a given subject reveal potential suicidality, then the Investigator should assess the clinical significance of such results. If a clinically significant risk of suicidality is identified for a subject, then the Investigator should discontinue the subject and implement appropriate treatment ([Section 6.5.4](#)).

Individual subject and aggregate safety data will be reviewed regularly throughout the study to determine whether the study should be stopped, modified, or continued based on the review of cumulative data. This review will include analysis of similar clinically significant laboratory findings/abnormalities, ECG abnormalities, vital sign abnormalities and AE's among subjects in order to assess all potential risks from blinded investigational product.

The Sponsor reserves the right to discontinue the study at any time for any reason. Such reasons may be any of, but not limited to, the following:

- Occurrence of AEs unknown to date in respect of their nature, severity, and duration or the unexpected incidence of known AEs

- Frequently-occurring, similar serious adverse events that increases risk for all subjects from continued participation in the study
- Frequently-occurring, similar clinically significant laboratory findings/abnormalities, ECG abnormalities, and/or vital sign abnormalities that increases risk for all subjects from continued participation in the study
- Medical, ethical, or business reasons affecting the continued conduct of the study

Regulatory authorities also have the right to terminate the conduct of the study in their region for any reason.

If the study is terminated for any reason, subjects remaining in the study will return to standard of care.

4.5.1 Discontinuation of Study Drug for Individual Subjects

The Investigator and Medical Monitor will review all laboratory, ECG, and related safety data regularly throughout the study for all individual subjects in order to determine whether any individual subject may continue to safely participate in the study. In general, either the Investigator or the Medical Monitor may discontinue the subject from the study at any time when any specific laboratory or ECG data change from Baseline indicates that the subject is placed at increased risk from continued participation in the study.

In rare instances, it may be necessary for a subject to permanently discontinue study drug. Study drug stopping criteria are described below. If a subject experiences any of the below events, it must be documented as an AE.

See [Section 4.5.2](#) for handling of subjects who discontinue and for any further evaluations that need to be completed.

4.5.1.1 Liver Chemistry Stopping Criteria

Discontinuation of study drug for abnormal liver tests is required by the Investigator when a subject meets one of the conditions outlined below. The Investigator can discontinue study drug in the presence of abnormal liver chemistries not meeting protocol-specified stopping rules if they believe that it is in best interest of the subject.

- Alanine aminotransferase (ALT) or aspartate aminotransferase (AST) $\geq 3 \times$ upper limit of normal (ULN)
 - if there is an elevation of $>2 \times$ ULN, the laboratory assessment should be repeated
 - If ALT or AST is $\geq 3 \times$ ULN, international normalized ratio (INR) should be tested

- If a subject is discontinued from the study because of ALT or AST $\geq 3 \times$ ULN, every reasonable attempt should be made to follow the subject until the value(s) normalize or until the Investigator deems it to be chronic or stable.
- Total bilirubin (TBL) $\geq 1.5 \times$ ULN
- Creatine kinase (CK)/creatine phosphokinase (CPK) $\geq 5 \times$ ULN for more than 1 week

4.5.1.2 Cardiovascular-Related Stopping Criteria

If a clinically significant finding of orthostatic hypotension, bradycardia, or change in QTcF, as defined below, is identified after enrollment, the Investigator or qualified designee and Medical Monitor will determine if the subject can continue in the study and if any change in subject management is needed.

- Orthostatic hypotension – decrease in systolic blood pressure (SBP) ≥ 20 mmHg or diastolic BP (DBP) ≥ 10 mmHg after transitioning from the supine position (after resting for 5 minutes) to standing at 1 or 3 minutes with or without symptoms such as light headedness or dizziness and not explained by dehydration, illness, or medications
- Significant bradycardia, defined as heart rate of ≤ 45 beats per minute (BPM) on an ECG, or pulse decrease of $\geq 25\%$ from Baseline with resulting heart rate < 60 BPM
- QTcF result > 470 ms for males and > 480 ms for females or QTcF increases ≥ 60 ms from Baseline

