	
30 days of Screening, or the need for such therapy during the study
 
Medical History, Laboratory Studies, Vital Signs, and Electrocardiograms
 
12. Has current evidence, or history within the previous 12 weeks prior to Screening, of a serious and/or unstable psychiatric, neurologic, cardiovascular, respiratory, gastrointestinal, renal, hepatic, hematologic, endocrinologic, or other medical disorder, that in the judgment of the Investigator and/or Medical Monitor would jeopardize the safe participation of the subject in the study
 
13. Had a malignancy in the last year, with the exception of nonmetastatic basal cell of the skin or localized carcinoma in situ of the cervix
 
14. Has any clinically significant laboratory abnormalities at Screening that in the judgment of the Investigator or Medical Monitor would jeopardize the safe participation of the subject in the study. Has one or more clinical laboratory test values outside the range specified below at Screening or Baseline:
 
aspartate aminotransferase (AST) $\geq 1.5 \times$ the upper limit of normal range (ULN)alanine aminotransferase (ALT) $\geq 1.5 \times$ ULNtotal bilirubin (TBL) $>$ULN range or has a known condition that is associated with hyperbilirubinemia (e.g. Gilbert's syndrome) 
15. Has moderate or severe renal impairment (estimated glomerular filtration rate [eGFR] $< 60 \text{ mL/min/1.73 m}^2$ from screening clinical laboratory tests)
 
16. Has an ECG QTcF result $> 480 \text{ ms}$ at Screening or Baseline
 
17. Has a history of uncontrolled hypertension, as defined by:
 
Systolic blood pressure $\geq 180 \text{ mmHg}$ or diastolic blood pressure $\geq 100 \text{ mmHg}$ at Screening or BaselineSystolic blood pressure of 160-179 mmHg or diastolic blood pressure of 100-109 mmHg at Screening or Baseline, AND a history of end-organ damage (including history of left ventricular hypertrophy, heart failure, angina, myocardial infarction, stroke, transient ischemic attack, renal failure, peripheral arterial disease and moderate to advanced retinopathy [hemorrhages or exudates, papilledema])
--	--

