6.5.3 Electrocardiograms

All 12-lead electrocardiograms (ECGs) will be complete, standardized recordings. A single 12-lead ECG will be performed at Screening, at Baseline (Week 0) both predose and 1 hour postdose (the first dose of the day), Week 1, Week 2, and Week 4 (EOT)/ET. A 1-hour window is permitted for the predose ECG; a 20-minute window is permitted for the postdose ECGs. Electrocardiograms should be performed prior to blood sampling (or at least 30 minutes after blood sampling) and vital signs but after pain assessments are completed.

The subject must rest in a supine position for 5 minutes before the ECG is obtained. ECG tracings (paper or electronic) will be reviewed and interpreted by a qualified clinician. All ECG tracings and results (ventricular rate, PR, QRS, QT, QTcF, and QTcB intervals) will be included in the subject's record.

At Screening, if the ECGs have a prolonged QTcF due to an identifiable cause, and it is medically appropriate to address that cause, a repeat ECG may be performed during Screening at the discretion of the Medical Monitor.

At Baseline (Week 0), a subject may be enrolled based on the review and interpretation of the ECG by a qualified physician. If the interpretation of the ECG indicates a QTcF outside of the allowable range, the subject will be discontinued from the study, but this will not be considered a protocol deviation.

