7 ADVERSE EVENTS

7.1 Specification of Safety Parameters

7.1.1 Definition of Adverse Event

An AE is defined as “any untoward medical occurrence in a patient or clinical study participant, temporally associated with the use of study drug, whether or not considered related to study drug”.

An AE can therefore be any unfavorable and unintended sign (e.g., an abnormal laboratory finding), symptom, or disease temporally associated with the use of a drug, without any judgment about causality or seriousness. An AE can arise from any use of the drug (e.g., off-label use, use in combination with another drug) and from any route of administration, formulation, or dose, including an overdose.

A suspected adverse reaction is any AE for which there is a reasonable possibility that the drug caused the AE.

AEs do not include the following:

- Stable or intermittent chronic conditions (such as myopia requiring eyeglasses) that are present prior to Baseline and do not worsen during the study
- Medical or surgical procedures (e.g., surgery, endoscopy, tooth extraction, transfusion). The condition that leads to the procedure is an AE if not present at time of consent, or scheduled surgery/procedure.
- Overdose of concomitant medication without any signs or symptoms will not be considered an AE, but if subject is hospitalized or has other serious criteria, the overdose shall be reported on the Sponsor’s Overdose Reporting form
- Hospitalization for elective surgery planned prior to study (situation where an untoward medical occurrence has not occurred)
- Pregnancy will not be considered an AE, but if it occurs, it will be reported on a pregnancy form

For subjects who discontinue from the study, AEs will be recorded from the time informed consent is obtained until 30 (+4) days after the last dose of study drug.

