14.1 Adverse Events

Adverse events will be coded using MedDRA dictionary, Version 24.0 or newer.

An AE (classified by preferred term) will be considered a treatment-emergent AE (TEAE) if started after first dose administration and no later than last dose date + 30 days. AEs reported on Day -1 based on Baseline (pre-dose) findings (e.g., clinically significantly abnormal vital signs, laboratory test results, or electrocardiogram parameters) will not be considered as TEAEs.

The event counts, the number, and percentage of subjects reporting TEAEs in each treatment group will be tabulated by system organ class (SOC) and preferred term; by SOC, preferred term, and maximum severity; and by SOC, preferred term, and relationship to study drug. If more than one TEAE occurs with the same preferred term for the same subject, then the subject will be counted only once for that preferred term using the most severe and most related occurrence for the summarization by severity and by relationship to study drug. The display in these tables will be sorted alphabetically by SOC and then by descending subject frequency for the preferred terms (counts from ACP-044 treated group) within each SOC.

The event counts, the number and percentage of subjects with any TEAEs will also be tabulated by preferred term without SOCs. This table will be sorted by descending subject frequency within ACP-044 treated group.

The incidence of most frequently reported (preferred terms reported by $\geq 5\%$ of subjects in any treatment group) TEAEs, SAEs reported after treatment start, TEAEs leading to discontinuation of study drug, and TEAEs related to study drug will be summarized by SOC, preferred term, and treatment group. The tables will be sorted alphabetically by SOC and then by descending frequency within each SOC in ACP-044 treated group. In addition, the incidence of fatal treatment-emergent AEs (i.e., events that cause death) will be summarized separately by SOC and preferred term.

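### Exclusion 16 admits men with QTcF of 471-480 ms, although section 4.5.1.2 flags any value above 470 ms in men for review, so an enrolled man can meet the on-study limit with no change from Baseline

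*Protocol*

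**What the plan says.** **Entry.** Exclusion 16 in Protocol section 4.2 reads "Has an ECG QTcF result >480 ms at Screening or Baseline". The synopsis gives the same limit. Neither separates the sexes. At the Baseline visit, section 6.5.3 adds only this: "If the interpretation of the ECG indicates a QTcF outside of the allowable range, the subject will be discontinued from the study". No lower limit for men is given anywhere.

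**On study.** Section 4.5.1.2 lists "QTcF result > 470 ms for males and > 480 ms for females" and joins it by *or* to a rise of at least 60 ms from Baseline. The lead-in is "If a clinically significant finding of orthostatic hypotension, bradycardia, or change in QTcF, as defined below, is identified after enrollment". What follows is a decision by the Investigator (or designee) and Medical Monitor on whether the subject can continue and whether management should change.

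**Recording and reporting.** Section 4.5.1, which introduces the stopping criteria, says "If a subject experiences any of the below events, it must be documented as an AE". SAP section 14.4 tabulates the same sex-specific limits, in a row separate from the rise of at least 60 ms.

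**The concern.** An eligibility limit should not admit a value that the trial's own safety rule flags as soon as it is measured again. For men it does. Two consequences follow.

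- A site may have to review, and under section 4.5.1 record as an AE, a QTcF that the entry rule accepted shortly before. Whether an unchanged value counts depends on how the site reads the lead-in, so sites can differ.
- Such a man is counted in the above-470-ms row of SAP section 14.4, because that row carries no condition on Baseline.

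What is at stake is consistent safety conduct and one descriptive ECG row.

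**Working it through.** **Step 1. Set the limits side by side.**

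| Criterion | Entry limit (section 4.2) | On-study limit (sections 4.5.1.1, 4.5.1.2) | Entry relative to on-study |
|---|---|---|---|
| QTcF, men | excluded if >480 ms | >470 ms | looser by 480 − 470 = 10 ms |
| QTcF, women | excluded if >480 ms | >480 ms | equal |
| ALT or AST | excluded if ≥1.5 × ULN | ≥3 × ULN | stricter |
| Total bilirubin | excluded if >ULN | ≥1.5 × ULN | stricter |
| Orthostatic drop | ≥20 mmHg systolic or ≥10 mmHg diastolic | same | equal |

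The overlap for men is 471-480 ms in whole milliseconds. A man at 475 ms at Baseline and 475 ms at Week 1 is eligible, has changed by 0 ms, and exceeds 470 ms. Because the two on-study conditions are joined by *or*, the absolute value is enough. Of the criteria with a numeric limit at both points, only QTcF in men has the looser limit at entry.

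**Step 2. How many men?** The documents give no QTcF distribution, so every input in this step is an assumption, shown over a range:

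- single male reading normal, mean 405-425 ms, SD 18-25 ms;
- within-subject SD *w* = 8-12 ms;
- 35-50% men;
- no drug effect;
- readings independent given the man's true value T, with variance SD² − *w*².

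From the documents: limits of 480 and 470 ms; eligibility checked at Screening and Baseline; 4 scheduled post-dose ECGs (1 hour after the first dose, Weeks 1, 2 and 4); 240 planned and 61 randomized.

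Let F(c) = Φ((c − T)/*w*), and let E[·] be the average over T. Then:

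- Eligible now: E[F(480)²].
- Eligible men with Baseline at 471-480 ms: E[F(480)·(F(480) − F(470))] / E[F(480)²].
- Of those, at least one of 4 post-dose readings above 470 ms: E[F(480)·(F(480) − F(470))·(1 − F(470)⁴)] / E[F(480)·(F(480) − F(470))].
- Expected men meeting the limit this way: N × share of men × the product of the two lines above.
- Currently eligible men excluded by a 470 ms limit at both visits: 1 − E[F(470)²] / E[F(480)²].
- Share of all men's post-dose crossings which that limit removes: 1 − E[F(470)²·(1 − F(470)⁴)] / E[F(480)²·(1 − F(470)⁴)].

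Results (ranges run over *w* and the share of men):

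| Mean / SD (ms) | Baseline 471-480 | At least 1 of 4 >470 | Men of 240 | Men of 61 | Excluded by fix | Crossings removed by fix |
|---|---|---|---|---|---|---|
| 405 / 18 | 0.013-0.014% | 12-40% | 0.001-0.006 | below 0.01 | 0.02-0.03% | 5-20% |
| 415 / 20 | 0.22-0.23% | 33-58% | 0.06-0.15 | 0.02-0.04 | 0.39-0.44% | 15-32% |
| 425 / 25 | 1.86-1.93% | 60-74% | 1.0-1.6 | 0.25-0.42 | 3.0-3.4% | 31-45% |

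Upper end worked through (425 / 25, *w* = 8, 50% men): 240 × 0.50 × 0.0186 × 0.738 = 1.6, and 61 × 0.50 × 0.0186 × 0.738 = 0.42.

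On the first post-dose ECG alone, 3-41% of men in the gap exceed 470 ms. Selection at a high reading brings regression to the mean: their average true QTcF is 443-468 ms.

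**The case against.** The strongest reply is that the text already limits the consequence. The lead-in asks for a clinically significant finding and speaks of a change in QTcF. Section 4.5.1 ties ECG-based discontinuation to a change from Baseline that signals increased risk. Section 7.1.1 keeps out of the AE definition stable chronic conditions "that are present prior to Baseline and do not worsen during the study". On that reading an unchanged 475 ms is looked at and the man continues. A lower trigger on drug than at entry could also be deliberate caution. Most of this stands, and it is why the point is minor. It does not remove the mismatch: the lead-in defers to the definition beneath it, which includes the absolute value, and no rationale for the looser entry limit is given.

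A reader might infer more than the documents support:

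- **That these men must stop treatment.** Section 4.5.1.2 opens a case decision and does not mandate a stop.
- **That SAP section 14.1 contradicts the AE rule.** Its exclusion covers "AEs reported on Day -1 based on Baseline (pre-dose) findings". The case here is a post-dose ECG, which that rule does not address.
- **That the ECG tables would mislead.** SAP section 14.4 summarizes categories at each visit and also tabulates change from Baseline, and SAP section 5 lists all data. A man already above 470 ms at Baseline can be identified.
- **That the fix would end unprovoked triggers.** In the model, 2.7-4.7% of men in the 425 / 25 case would still cross 470 ms by chance after the fix.

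Two further objections are fair. The count spans three orders of magnitude, and only the most extreme assumed distribution reaches one man. And the heart-rate limit of 45 bpm or below in section 4.5.1.2 has no entry counterpart at all, so an unchanged Baseline value could meet that one too; the fix does not address it.

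**Conclusion.** The mismatch holds and follows directly from the stated limits, without any assumption: a 10 ms band, men only, in which an eligible subject meets an on-study review limit with zero change. Its effect is small. It concerns review and AE recording that rest on judgment and may differ between sites, plus one descriptive ECG row with adequate context around it. Discontinuation is not forced and efficacy is unaffected.

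The expected number, 0.001-1.6 men of 240 and at most 0.4 of 61, rests entirely on the assumed distributions, independent readings and no drug effect; the documents cannot narrow it. Severity: minor.

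**What to change.** Change exclusion 16 in section 4.2 and in the synopsis to: *QTcF >470 ms for men or >480 ms for women at Screening or Baseline.* Leave section 4.5.1.2 unchanged. Raising the on-study limit for men to 480 ms would also close the gap, but by weakening a safety trigger.

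The cost is one line in two places and no new procedure. The edit loses men who read 471-480 ms at either visit, 0.02-3.4% of currently eligible men under the assumed distributions. It removes only about 5-45% of chance post-dose crossings in men, so its merit is consistency between the two rules.

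A flag in the SAP section 14.4 output for subjects already above the sex-specific limit at Baseline is optional and mostly redundant with the by-visit, change-from-Baseline and listing outputs. The trial was terminated on 8 August 2022, before SAP version 1.0 of 21 September 2022, so the eligibility edit applies to the plan as written and to any reuse of this text.
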